3. N/A
4. See Appendix 2.

B. Screening Interview/questionnaire: N/A

C. Informed consent process and timing of obtaining of consent

- 1 A study team member will provide a written informed consent form for patients and obtain their written informed consent.
- 2 The patient will be provided with a study introduction letter and written consent form. They will be able to review these independently or will have the option to have the papers read to them if requested. The patient will then have the opportunity to ask questions if they would like, but no coercion will take place during this process. The consent forms will be kept in a secure, locked location on the burn unit to ensure that the study participants remain confidential.

3. Only subjects who have been determined in the course of their routine medical care to be of capacity to make their own medical decisions will be included in the study.

D. Alternatives to Participation: If patients choose not to participate in this research study, they will undergo routine medical care, including the use of lidocaine with epinephrine for treatment of their STSG donor site and routine use of pain medications postoperatively. Their medical care will not be compromised if they choose not to participate in the study.

E. Costs to Subjects: This study involves the use of approved, standard of care operative medications that are included in the operative cost. Patients who do not have insurance will be eligible to participate in the study as we routinely manage patients who do not have insurance with the same standard of care as patients who do not have insurance. See completed qualification form.

F. How new information will be conveyed to the study subject and how it will be documented: If new or unexpected information is discovered during the course of the study, study subjects will be notified in writing at the address available in their medical record.

G. Payment, including a prorated plan for payment: There will be no payment to study subjects who choose to participate in this study.

H. Payment for a research-related injury: Subjects who sustain an adverse reaction to the medication will be managed with routine medical care but will not receive monetary compensation.

IV. Data Collection and Protection

A. Data Management and Security:

1. The study team members will have access to the data.
2. Patient assessment scales collected by nursing staff will be stored in a secure, locked location until collected by study staff. All data collected will be recorded using the KU RedCAP database. Study subjects will be deidentified in the RedCAP database.
3. subjects will not be identifiable directly and will be coded.
4. The study coordinator will have access to the code.
5. Patient medical record number will be linked to the code, and this will be used to identify study subjects during data collection.
6. Data will be stored on the secure KU RedCAP database.
7. N/A
8. N/A

B. Sample / Specimen Collection: N/A

C. Tissue Banking Considerations: N/A

D. Procedures to protect subject confidentiality: Patients will be identified by nursing staff as enrolled in the study to collect the post-operative pain scale assessments. Nursing staff are experienced in maintaining patient confidentiality as this is an expectation with all levels of care they provide. Following the data collection process, the study subjects will be deidentified to maintain their confidentiality.

E. Quality Assurance / Monitoring

1. Data that is collected will be self-reported from patients or collected as objective data from the medical record. No subjective assessments will be done by study team members. There is a chance that study subjects could intentionally falsify their pain scores for secondary gain, for example, to receive more narcotic pain medications. To limit this potential, we will not be including patients in the study who have ongoing opioid use for chronic pain or abuse prior to admission.
2. There are no plans for third party monitoring of this study.

V. Data Analysis and Reporting

- A. Statistical and Data Analysis:** Differences between groups will be assessed using Chi square test for categorical variables and Student's t test for two means. Confidence intervals will be calculated to 95% and a p value of less than 0.05 will be considered statistically significant. Final statistical analysis will be conducted by statistician. Interim analysis is planned for at the half way point of the study (20 patients completed). Interim statistically analysis will be conducted by Co-Investigators.
- B. Outcome:** We expect that the experimental group will have decreased pain scores compared to the control group. We estimate a 2 point difference in pain scores for the STSG donor site and that this difference will occur at 1, 2 and 3 days post-op. We expect that opioid consumption and time to first opioid dose will also be decreased in the study group. Our power analysis calculation based on pain score decrease aims to enroll 40 patients in the study and this is our anticipated study end point.
- C. Study results to participants:** Study subjects may submit a written request to receive study results after completion of the study. If requested, results will be mailed to the study subject after completion of data analysis.

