3. N/A

II. Research Plan and Design

- A. Study Objectives:** The objective of this study is to determine if use of liposomal bupivacaine (Exparel) decreases postoperative pain at the donor site compared to lidocaine for split thickness skin grafting in patients with burn injuries. In addition, we aim to identify if use of Exparel at the donor site for split thickness autografting decreases opioid pain medication consumption postoperatively compared to use of lidocaine at the donor site in patients with burn injuries.
- B. Study Type and Design:** This study will be a prospective, randomized controlled trial. Study subjects will be blinded to their randomization to avoid bias. The control group will undergo split thickness autografting using the standard protocol, involving injection of lidocaine with epinephrine at the donor site. The experimental group will undergo injection of liposomal bupivacaine (Exparel) at the time of harvest of the skin graft. Baseline pain levels will be obtained for all subjects using a validated pain assessment scale, the

Visual Analog Pain Scale. Postoperatively, time to first opioid pain medication (excluding immediate postoperative recovery from anesthesia), total opioid consumption on a daily basis, and donor site interval pain scores using a validated pain assessment scale will be obtained. The experimental group will then be compared to the control group to determine if there is a significant difference in pain levels, time to first opioid, and overall opioid consumption between the two groups.

C. Sample size, statistical methods, and power calculation

[figure not shown]
1. Patients will be randomized using a computerized random number generator with 1:1 randomization. Differences between groups will be assessed using Chi square test for categorical variables and Student's t test for two means. Confidence intervals will be calculated to 95% and a p value of less than 0.05 will be considered statistically significant.
2. Only subjects will be blinded to their randomization group. Study subject number will be linked to their randomization group. Blinding may be broken if the subject experiences an adverse reaction to the medication utilized for their group so that they are aware that they cannot receive the medication in the future.

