3. We anticipate a reduction in pain scores by 2 points with SD 2.5 in the experimental group. Power analysis for 80% power yields 25 patients per group. We will aim to enroll a total of 50 patients, 25 in each group.

D. Subject Criteria (See Vulnerable Populations appendix, if applicable):

1. Inclusion criteria: State the criteria for inclusion in the study in a specific and detailed manner.
 - E. Age \geq 18 years, English or Spanish speaking, Burn injury with the following parameters: $\leq 20\%$ TBSA partial thickness, $\leq 5\%$ TBSA deep partial or full thickness, first skin autografting procedure for hospitalization, donor site anterior or lateral thigh
2. Exclusion criteria: State the criteria for excluding potential subjects from the study in a specific and detailed manner.
 - E. Chronic pain syndrome on opioid pain medications at baseline, $>20\%$ TBSA partial thickness burn, $>5\%$ TBSA surgical area of burn injury (deep partial or full thickness injury), pregnant women, age < 18 , not first skin autografting procedure during hospitalization, allergy to lidocaine or other local anesthetics, burns to anterior thighs, inability to give informed consent
3. Withdrawal/Termination criteria: Include the specific circumstances in which the subject's participation will be terminated by the investigator. Include any necessary safety precautions to be applied to those who withdraw (tapering drug doses, evaluative x-ray, etc.)
 - E. Serious adverse reactions to lidocaine or liposomal bupivacaine including cardiac event, arrhythmia, seizure, anaphylaxis, and loss of limb. Subjects who experience these reactions will be medically stabilized and undergo standard work-up based upon symptoms. The subject will be unblinded and the medication administered will be documented in their medical record as an allergy. They will be withdrawn from the study and the adverse reaction will be reported to the IRB within 24 hours.
4. Clarify whether a study subject may participate in another research study while participating in this research study.
 - E. Subjects may participate in additional research studies as long as study protocols do not interfere with one another. For example, subjects may not be enrolled in a study comparing experimental pain management or alternative methods of skin autograft harvest.

E. Specific methods and techniques used throughout the study

1. Laboratory tests: No laboratory specimens will be required for participation in this study.

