Appendix III: Data collection From Chart Review

Age at time of surgery:

Gender:

Race:

Total Burn TBSA:

Deep partial thickness/ full thickness burn percentage:

Time to first opioid from minutes post-op following completion of post-operative recovery period:

First opioid dose:

First opioid route:

Total opioid administered in morphine equivalents for 72 hours post-operatively:

Non-opioid adjunct medication administration:

Anesthesia occurrences in first 72 hours post-op:

Time of donor site dressing open to air:

Time of first donor site dressing change:

[figure not shown]
Prior to admission opioid use:

Donor site size:

Donor site location:

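### The 72-hour opioid total is compared by an unadjusted t test, although it includes opioids taken for the burn itself and burn size and age are already recorded

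*Combined protocol and SAP*

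**What the plan says.** Sections II.C.1 and V.A carry the same sentence: "Differences between groups will be assessed using Chi square test for categorical variables and Student's t test for two means". Means are therefore compared by a t test and categorical variables by chi-square. No covariate, regression model or stratified analysis is named anywhere. On allocation, II.C.1 says only "Patients will be randomized using a computerized random number generator with 1:1 randomization"; it mentions no stratification.

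The chart-review form in Appendix III has fields for age at surgery, "Total Burn TBSA" and "Deep partial thickness/ full thickness burn percentage". Age and burn extent are also eligibility criteria in II.D. The analysis sections give none of these a role.

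Under II.E.2.d, narcotic use is taken from the medical record in morphine equivalents, and Appendix III records a 72-hour total. II.E.3 explains that the study pain scale asks about the donor site alone, whereas routine assessment asks about pain overall. The opioid measure has no such restriction.

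**The concern.** The second aim is to show lower opioid use after liposomal bupivacaine. The injection acts at the donor site, but the recorded total covers opioids given for any reason, including pain from the burn wound. Burn size is therefore a plausible source of patient-to-patient variation in this outcome that has nothing to do with treatment. With 20 to 25 patients per arm, simple randomisation can leave the arms visibly different in burn size, and neither the design nor the analysis deals with that. Only subjects are blinded (II.C.2), and the co-investigators run the interim analysis (V.A), so an adjustment chosen after an imbalance is seen would carry little weight. At stake are the precision of the opioid comparison and how it can be read if the arms turn out unequal.

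**Working it through.** **Inputs.** From II.C.3: "We anticipate a reduction in pain scores by 2 points with SD 2.5 in the experimental group". The same item sets 80% as the target and gives 25 per arm, 50 in all. From II.C.1: "a p value of less than 0.05 will be considered statistically significant" (two-sided is assumed, since the documents do not say). V.B gives a total of 40 instead of 50, so both 25 and 20 per arm are shown. The documents give no R-squared for any covariate and no SD or target effect for opioid use. R-squared is therefore assumed over 0 to 0.30, and the planned standardised effect of 2 / 2.5 = 0.8 stands in for the opioid effect.

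**The plan's own figure.** n = 2 × (1.96 + 0.842)² × 2.5² / 2² = 24.5, so 25 per arm; the stated size reproduces. By the exact noncentral t, the unadjusted test has 79.1% power at 25 per arm and 69.3% at 20.

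**Chance imbalance.** The standardised difference between arms in one covariate has SE = √(2/n): 0.283 at n = 25 and 0.316 at n = 20. P(|difference| > 0.5 SD) = P(|Z| > 0.5/SE):
- n = 25: P(|Z| > 1.768) = 7.7%
- n = 20: P(|Z| > 1.581) = 11.4%

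A 0.5 SD imbalance in a covariate with correlation r to the outcome shifts the difference by 0.5 × r outcome SDs. This is 0.10 SD at r = 0.2 and 0.25 SD at r = 0.5 (both assumed), against an effect of 0.8 SD.

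**Power with two covariates (total TBSA and age).** Residual SD = 2.5 × √(1 − R²), with df = 2n − 2 − 2. Chance correlation between covariates and arm inflates the variance by (2n − 3)/(2n − 3 − 2), which is 47/45 = 1.044 at n = 25 and 37/35 = 1.057 at n = 20. The noncentrality is 2 / (residual SD × √(2/n × inflation)).

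Example at n = 25 and R² = 0.10: residual SD = 2.372; SE = 2.372 × √(0.08 × 1.044) = 0.686; noncentrality = 2.917 on 46 df; power = 81.5%.

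| R² (assumed) | 25 per arm | 20 per arm |
|---|---|---|
| unadjusted | 79.1% | 69.3% |
| 0 | 77.3% | 66.8% |
| 0.10 | 81.5% | 71.4% |
| 0.20 | 85.7% | 76.3% |
| 0.30 | 89.9% | 81.6% |

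If the covariates explain nothing, the loss is 79.1 − 77.3 = 1.8 points at 25 per arm and 69.3 − 66.8 = 2.5 points at 20. Adjustment breaks even at an R² of about 0.04 and 0.06 respectively. Simulation of 20,000 trials per scenario, at R² of 0, 0.10 and 0.30, agrees with the table to within 0.6 points.

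**Validity of the planned test.** Simulated type I error of the unadjusted t test is 4.8% to 5.2%.

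**The case against.** The strongest reply is that nothing in the plan is invalid. After randomisation the unadjusted t test keeps its error rate, and its confidence interval already allows for chance imbalance on average. That stands: a reader might infer that the planned test is biased, and it is not.

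The second reply is that adjustment is not free and need not help. A reader might suppose that it costs only the degrees of freedom. It also costs the variance inflation shown above, so covariates that predict little lose power. The documents do not show that burn size and age pass the break-even, and the eligibility limits (20% TBSA partial thickness, 5% deep or full thickness) narrow the range and may weaken burn size as a predictor. This also stands, and is why the model should be small and the gain stated as conditional.

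Third, it is tempting to extend the argument to donor-site pain. The documents do not support that. The pain scale concerns a thigh wound made at surgery, burns to the anterior thighs are excluded, and nothing shows that burn size elsewhere predicts pain there. The pre-operative pain score is the covariate that the protocol expressly records beforehand, but whether to use it for the pain endpoint is a separate question.

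Fourth, adding deep-burn percentage and quoting a joint chance of imbalance across three covariates would assume independence, which overlapping burn measures are unlikely to have. Only the single-covariate probabilities are used here.

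Last, Appendix III gives no time at which its fields are abstracted, so a reader should not take them as documented pre-surgery values. Burn extent is assessed for eligibility, so a pre-surgery value should exist, but the plan needs to say that this is the one to use.

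**Conclusion.** The concern holds for the opioid total, as a missed low-cost improvement and not as an error. The outcome includes opioids for burn-wound pain, a plausible predictor is on the form, and neither randomisation nor analysis uses it. The size depends on an R-squared that the documents do not give. Over 0.10 to 0.30, two covariates would add about 2 to 11 points of power at 25 per arm and about 2 to 12 at 20, against a loss of 1.8 and 2.5 points if they explain nothing. These figures borrow the 0.8 SD effect planned for pain and assume normally distributed residuals and a two-sided 5% test. For donor-site pain, adjusting for burn size is optional.

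**What to change.** In V.A and II.C.1, make the main analysis of the 72-hour opioid total a linear model with treatment, total TBSA and age. State that both covariates take values established before surgery and that the list is fixed before any outcome is seen, including at the interim look. Keep the unadjusted t test as a supportive analysis. Leave out deep-burn percentage, which overlaps total TBSA, and donor-site size, which is set in theatre by staff who know the arm.

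The cost is a short change of wording, a timing rule for the TBSA field in Appendix III, and the small power loss above if the covariates prove uninformative. No new measurements or patients are needed.

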- 4. Describe how the lead investigators will ensure that all participating sites use the IRB-approved version of the protocol, consent, recruitment materials and other study documents. N/A
- 5. Describe how the lead investigators will communicate with and disseminate new information to other sites (e.g., training meetings, regularly-scheduled conference calls, notifications, etc.) N/A
- 6. Describe how the lead investigator will assess protocol compliance, unanticipated problems and adverse events at other sites. N/A
- 7. Name the member of the KUMC study team who will be the point of contact to coordinate oversight and communication with the sites. N/A

J. Community-Based Participatory Research (if applicable): N/A

- 1. Participants and the nature of their involvement: N/A
- 2. Cultural issues: N/A
- 3. Origin of the research question: N/A
- 4. Risks and Benefits: N/A
- 5. Study Description and Process: N/A
- 6. Return of results: N/A
- 7. Sustainability: N/A

K. Personnel who will conduct the study, including:

- 1. Indicate, by title, who will be present during study procedure(s):

Study personnel may be involved in the study procedures, including patient consent, assignment of study group, and accessing of the patient's medical record to obtain information related to opioid administration

Administration of liposomal bupivacaine or lidocaine will be by an attending burn surgeon or their designated resident, physician's assistant, or nurse practitioner

Pain scale assessment will be completed by the patient's bedside nurse (RN)

- 2. Primary responsibility for the following activities, for example:

- a. Determining eligibility: study coordinator, PI, co-investigators
- b. Obtaining informed consent: study coordinator, PI, co-investigators
- c. Providing on-going information to the study sponsor and the IRB: study coordinator
- d. Maintaining participant's research records: study coordinator, co-investigators
- e. Completing physical examination: co-investigators, PI, bedside nursing staff
- f. Taking vital signs, height, weight: nursing staff
- g. Drawing / collecting laboratory specimens: N/A
- h. Performing / conducting tests, procedures, interventions, questionnaires: nursing staff, co-investigators, principal investigator, study coordinator
- i. Completing study data forms: study coordinator, co-investigators
- j. Managing study database: co-investigators, study coordinator

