L. Assessment of Subject Safety and Development of a Data and Safety Monitoring Plan

- 1. Elements of the plan include:
 - a. Persons/groups who will review the data (study team; independent safety monitor, data monitoring committee or formal DSMB): The study team including the study coordinator will routinely monitor the study data to assess for patient safety issues or unanticipated patient events.
 - b. Data/events that will be reviewed: adverse events, pain assessment, opioid usage
 - c. Frequency of review: A formal review will be conducted at the midpoint of the study; additional reviews can be completed as needed in the event of any unanticipated event or concerns from study team members
 - d. Types of analyses to be performed: statistical analysis of data to determine if endpoints of study have been met.
 - e. Safety-related triggers that would cause the PI to stop or alter the study: presence of significant adverse events such as loss of limb or death; significant increase observed in pain and opioid usage in experimental group compared to control group
- 2. Adverse Events that occur during the course of the study will be documented. For each recorded event, the documentation will include the event's onset and resolution date (if the event has resolved), the frequency and severity of the event, a summary of any action taken as a result of the event (both in regard to any treatment given and to any change in dosing with the test article), and an assessment of the event's relationship to the test article.
 - a. Non-serious Adverse Events
 - 1. A non-serious adverse event is defined as a change from baseline (pre-treatment) in a subject's medical health that is not life-threatening, does not require hospitalization, does not prolong a current hospitalization, and is not disabling. Non-serious adverse events that may occur with the use of liposomal bupivacaine according to the FDA are hypoesthesia, hypotension, pain, drug ineffectivity, nausea, bradycardia, drug interactions due to medication error, nerve palsy, and erythema. These events all

occur at rates less than or equal to other medications marketed for similar indications, including lidocaine.

b. Serious Adverse Events- Serious Adverse Events that are suspected to be related to the test article and are unexpected (not identified in the product-package insert), will be reported to IRB and to the manufacturer of the test article within 24 hrs of the investigator's knowledge.

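### The midpoint between-group analysis is assigned to co-investigators who also enrol patients and manage the data, and nothing limits who sees the result

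*Combined protocol and SAP*

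**What the plan says.** All references are to the combined protocol and SAP.

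- **Who analyses.** V.A places an interim analysis at 20 completed patients and states: "Interim statistically analysis will be conducted by Co-Investigators". The contrast is in the same paragraph: "Final statistical analysis will be conducted by statistician".
- **What the analysts also do.** II.K.2 lists, among other duties, "Determining eligibility: study coordinator, PI, co-investigators". It also names the co-investigators for obtaining consent, maintaining research records, completing data forms and managing the database, and for a share of procedures and questionnaires.
- **What the midpoint look covers.** II.L.1.b: "Data/events that will be reviewed: adverse events, pain assessment, opioid usage". II.L.1.d gives the analysis as "statistical analysis of data to determine if endpoints of study have been met". One trigger in II.L.1.e is a "significant increase observed in pain and opioid usage in experimental group compared to control group".
- **Who is blinded and who has access.** II.C.2 blinds subjects only and links subject number to group. IV.A.1 gives study team members access to the data. II.L.1.a leaves review to the study team, and IV.E.2 says no third-party monitoring is planned.
- **Who collects pain scores.** II.K.1 gives the pain scale to the bedside nurse. IV.E.1 says study team members make no subjective assessments. The form in Appendix IV is marked by the patient.

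**The concern.** Knowing one patient's arm is different from knowing which arm is ahead. The first is unavoidable here for the staff who inject the study drug. The second arises only because the comparative analysis is done inside the team that is still recruiting.

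The two aims are donor site pain, a self-reported score, and opioid consumption. V.B shows that the team already expects the experimental arm to do better on both. An interim result from this trial would add to that expectation while recruitment continues. Results cannot be withdrawn once seen, so the point has to be settled before the look. A statistician is already in the plan, and II.K.2 gives that role no part in enrolment or data handling. Leaving the look with the co-investigators is therefore an avoidable exposure.

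**Working it through.** The main check is to set the sections side by side. The only arithmetic is the share of patients still to come.

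1. **Are the analysts the same people who run the trial?** Yes. V.A names the co-investigators for the interim. II.K.2 items a, b, d, i and j name them for eligibility, consent, records, data forms and database, and item h lists them with others for interventions and questionnaires.

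2. **Is the look by arm?** V.A does not use that term, so this is an inference, but a firm one. The only tests specified are between groups: "Differences between groups will be assessed using Chi square test for categorical variables and Student's t test for two means". Whether endpoints have been met cannot be judged from pooled data, and the pain and opioid trigger in II.L.1.e compares experimental with control. I take the interim analysis in V.A and the midpoint review in II.L.1.c to be the same look.

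3. **Does anything stand between the result and the recruiting team?** No section does. Blinding covers subjects only (II.C.2), the team has data access (IV.A.1), the team is the reviewing body (II.L.1.a), and no rule limits circulation.

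4. **How many patients are still to come?**
   - Inputs: look at 20 completed (V.A); planned total 40 (V.B) or 50 (II.C.3).
   - The plan's own figure: V.A calls 20 patients the half-way mark. 20/40 = 50%, which agrees with V.B. Against II.C.3, 20/50 = 40%, and half would be 25. The two totals need reconciling in any case, so both are carried here.
   - Remaining share = (N − 20)/N. For N = 40: (40 − 20)/40 = 20/40 = 50%. For N = 50: (50 − 20)/50 = 30/50 = 60%.
   - These are upper limits on patients still to be enrolled, because anyone enrolled but not completed at the look has already been recruited. Pain assessment lasts three days (II.E.2.d), so that number should be small. It grows if accrual continues while the analysis is prepared, which the documents do not address.

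5. **What do the 50% and 60% measure?** They count patients enrolled after the result could be known. They do not measure bias, and no input in the documents allows its size to be calculated.

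6. **Which safeguards already exist?** Nurse collection (II.K.1), self-report (IV.E.1, Appendix IV) and subject blinding (II.C.2) protect the scoring step in part. They do not cover eligibility, consent or data handling, and II.K.2.h still lists co-investigators for questionnaires.

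**The case against.** A reader might infer that the rest of the trial would drift toward the interim result, so that 50–60% of the data would be compromised. The documents do not support that reading, for four reasons.

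- **Scoring.** Blinded patients mark their own pain and a bedside nurse handles the form. Nothing says the nurses receive interim results. This stands as a real, though partial, safeguard.
- **Approach and consent.** Knowing which arm leads could change whom staff approach or what they say at consent. Both act before treatment, on patients who will be blinded. They would shift both arms alike unless the next allocation could be foreseen, and the documents do not show that it could. Case mix may change, but the between-arm difference is not thereby pushed in one direction. This also stands.
- **Opioids.** No section says that co-investigators prescribe or give postoperative opioids. The opioid role that II.K.1 states for study personnel is obtaining information from the medical record. An effect by this route is possible but not shown.
- **Monitoring.** IV.E.2 says that no third-party monitoring is planned. It does not forbid independent handling of one analysis.

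A further objection is practical: the team is unblinded and manages the database, so changing the analyst alone would leave it able to make the same comparison. That is correct, and the fix has to reach data access as well.

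What survives is narrower. Unblinded staff with enrolment and data duties produce the comparative result themselves, and no rule limits who sees it.

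**Conclusion.** The point holds as a weakness in trial conduct. The people who select and consent patients and manage the data would learn the interim direction on pain and opioid use with up to 20 of 40 or 30 of 50 patients still to be enrolled, less any enrolled but not yet completed. It is an avoidable risk, not a demonstrated bias, and its size cannot be computed from the documents.

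The conclusion assumes that the V.A interim analysis and the II.L.1 midpoint review are one look, that the look is by arm, and that recruitment continues afterwards. The first two follow from the wording of II.L.1 and V.A but are not stated outright. The proper label is a cheap improvement.

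**What to change.** - **V.A and II.L.1.** Assign the midpoint comparison to the statistician already named for the final analysis. That person tells the principal investigator and team only whether a II.L.1.e trigger has been met. II.L.1.e attaches no specific threshold to its pain and opioid trigger, so the sponsor should state before the look how it will be judged.
- **IV.A.1 and II.K.2.j.** Bar the study team from viewing or tabulating pain and opioid outcomes by arm before database lock. Without this, the link between subject number and group (II.C.2) lets the team rebuild the comparison. The team keeps review of individual adverse events and of data pooled over arms.

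The cost is protocol wording, a database access setting and a few hours of the statistician's time. The small downside is that the team cannot watch efficacy by arm during the trial. Staff will still know individual patients' arms, so the change reduces the exposure and does not remove it entirely.
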